7.7	In multi-center investigations, the minimum and maximum number of subjects to be included for each center.....	46
8	Data Management.....	47
8.1	Data Management Plan	47
9	Document Retention.....	48
10	Amendments to Clinical Investigation Plan	49
11	Publication Policy	50
12	Investigation Organization.....	51
12.1	Investigation Management / Sponsor.....	51
12.1.1	Sponsor Responsibilities	51
12.2	Clinical Investigators	52
12.2.1	Investigator’s responsibilities.....	52
12.2.2	Clinical Coordinating Investigator.....	53
12.2.3	Source Data and Patient Files.....	53
12.3	Boards.....	54
12.3.1	Steering Committee (SC)	54

12.4	Outsourcing of duties and functions.....	54
12.4.1	Echo CoreLab (EchoCL)	54
12.4.2	ECG Core Lab (ECG CL)	54
12.4.3	Fluoroscopy Images Core Lab (FCL)	54
12.4.4	EuroQoL (EQ-5D Questionnaire)	54
12.4.5	MAPI Trust (MLWHF Questionnaire).....	55
13	Bibliography.....	56
	Appendix A: Abbreviations	59
	Appendix B: Declaration of Helsinki	61
	Appendix C: Device Manual.....	66
	Appendix D: Data Collection Method	67
	Appendix E: Guidelines.....	70

1 Synopsis

Title:	“MOre REsponse on Cardiac Resynchronization Therapy (CRT) with MultiPoint Pacing (MPP)”
Acronym:	MORE-CRT MPP
Purpose:	The purpose of this Clinical investigation is to assess the impact of the Multi Point Pacing (MPP) feature at 12 months in the treatment of patients not responding to standard Cardiac Resynchronization Therapy (CRT) after 6 months. Due to a large number of combinations of parameters available for MPP programming, the MPP feature will be evaluated under two scenarios: (1) without mandating MPP programming parameters, and (2) with mandated MPP programming parameters.
Objectives:	
Primary Objective To demonstrate that the activation of the MPP feature will increase the rate of CRT responders in patients that are classified as non-responders at 6 months of follow up.
 
Secondary Objectives To assess the impact of the MPP feature on patients’ functional and clinical status, as well as complication free survival time.

Endpoints:	
Primary Endpoint (assessed at 12 months) Percentage of non-responder patients converted to responders after 6 months of MPP feature turned ON compared to baseline, as measured by Left Ventricular End Systolic Volume (LVESV) reduction of at least 15%.
 
Secondary Endpoints (assessed at 12 months)
 
 • Reduction of LVESV between baseline and 6 month visit • Packer’s Clinical Composite Score evaluation between the baseline and the 12 month visit; and between the 6 month and the 12 month visit • Reverse LV remodelling, measured as changes in LVESV, LVEDD and LVEF • NYHA Class changes • 6 minutes walking test changes • Quality of Life (MLWHF and EQ-5D) changes
Design:	
This study is designed as a Prospective, Randomized, Multi-center Trial.
 
Data will be collected at Enrollment, Baseline, Implant Procedure, Patient Classification, 6 Months and 12 Months Follow-Up.
 
During the Enrollment visit, the Informed Consent Procedure will be performed and the Inclusion/Exclusion criteria verified.
 
During the Baseline visit the demographic data, medical history, clinical data and procedure details will be collected.
 
After the Implant Procedure, the Patient Classification will be performed in

	
order to identify the Qualified Subjects that will constitute the Study Population.
 
During the 6 Months visit, the subject’s response to CRT will be evaluated according to LVESV reduction:
 
 • Subjects with a LVESV reduction of at least 15% will be classified as Responders: those subjects will terminate their participation to the study and return to the center’s standard practice. • Subjects with a LVESV reduction less than 15% will be classified as Non Responders: for those subjects the MPP feature will be activated according to randomization result and they will be followed up until 12 Months visit. 
During the 12 Months visit, the percentage of non-responder subjects converted to responders after 6 months of MPP feature turned ON will be assessed:
 
 • Subjects with a LVESV reduction of at least 15% between Baseline and 12 Months will be classified as Responders. • Subjects with a LVESV reduction less than 15% between Baseline and 12 Months will be classified as Non Responders. 
The investigation will be conducted in up to 250 centers worldwide.
 
[REDACTED]
 
[REDACTED]
 
[REDACTED]

Devices used:	
All subjects will be implanted with a CE-approved St. Jude Medical CRT device (CRT-D or CRT-P) compatible with MultiPoint Pacing feature and St. Jude Medical quadripolar left ventricular lead.
 
Any commercially available and CE marked right atrial and right ventricular leads can be used in this investigation for both treatment arms. During the follow ups, implanted devices will be checked with Merlin® Patient Care System (model 3650 or newer, software version 17.2.1 or newer) programmer.
 
All of the devices used in this investigation, have received appropriate regulatory certification (and are market released).

Subject Population:	
Patients with Heart Failure that meet current ESC or ACCF/AHA/HRS Class I or IIa indications for CRT implant.

Patients presenting at the investigational site can be screened by a member of the investigational team previously trained on the CIP and delegated to do so. Patients who do not meet the inclusion/exclusion criteria are not eligible to participate in this investigation.

Patients meeting the inclusion/exclusion criteria will be fully informed about the investigation and will be asked to participate in the investigation. If the patient agrees, a duly signed and dated, EC and Sponsor approved, Patient Informed Consent form will be obtained.

Inclusion Criteria:

Eligible patients will meet ALL the following:

- Meets the current ESC or ACCF/AHA/HRS Class I or Class IIa indications for CRT implant (including upgrades from single or dual chamber ICDs)
- Must be willing and able to comply with study requirements
- Must indicate their understanding of the study and willingness to participate by signing an appropriate informed consent form

Exclusion Criteria:

Patients will be excluded if they meet ANY of the following criteria:

- Already had a CRT device implanted
- Myocardial Infarction, unstable angina within 40 days prior the enrollment
- Recent cardiac revascularization (PTCA, Stent or CABG) in the 4 weeks prior the enrollment or planned for the 3 months following
- Cerebrovascular Accident (CVA) or Transient Ischemic Attack (TIA) in the 3 months prior the enrollment
- Primary valvular disease requiring surgical correction
- Atrial Fibrillation:
 - Persistent AF at the time of enrollment
 - Permanent AF not treated with AV node ablation within 2 weeks from the CRT implant
 - History or incidence of Paroxysmal or Persistent AF within 30 days prior the enrollment
- Unable to comply with the follow up schedule
- Less than 18 years of age
- Pregnant or are planning to become pregnant during the duration of the investigation
- Classification of Status 1 for cardiac transplantation or consideration for transplantation over the next 12 months
- Undergone a cardiac transplantation
- Life expectancy < 12 months
- Currently participating in any other clinical investigation

1.1 Investigation Flow Chart

[figure not shown]

Figure 1: Flow Chart

1.2.2 Coordinating Clinical Investigator

[REDACTED]
[REDACTED]
[REDACTED]
[REDACTED]
[REDACTED]
[REDACTED]
[REDACTED]
[REDACTED]

2 Background

Heart failure (HF) is an abnormality of cardiac structure or function leading to failure of the heart to deliver oxygen at the rate commensurate with the requirement of patient. European Society of Cardiology (ESC) 2012 guidelines defined HF as a syndrome in which patients have typical symptoms (e.g. breathlessness, swelling and fatigue) and signs (elevated jugular pressure, pulmonary crackles and displaced apex beat) resulting from an abnormality of cardiac structure or function¹.

HF is a varied clinical syndrome with complex pathophysiology, which continues to be defined, and often begins with a primary injury to the myocardium. Patients with HF experience decreased exercise capacity, inability to perform activities of daily living, diminished quality of life and an increased early mortality.

It is estimated that in the Western world more than 20 million patients suffer from end-stage HF. This indicates that the prevalence of this syndrome is 2-2.5% overall, increasing up to 10% among persons 70 years of age or older².

HF is a major threat to public health affecting an estimated 14 million individuals in Europe and it is estimated that 50% of people diagnosed with HF will die within 5 years¹⁻³.

Cardiac resynchronization therapy (CRT) using biventricular (BiV) pacing has been developed to restore synchrony in HF patients with delayed ventricular activation, predominantly of the left ventricle (LV). Studies have demonstrated that simultaneous or sequential BiV pacing restores the synchrony of contraction, reduces mitral regurgitation, and improves cardiac output^{4, 5}. Several landmark clinical trials published in the past few years have provided compelling evidence that CRT can produce significant clinical benefits, including improvements in patients' HF symptoms, quality of life, reduced HF hospitalization, and echocardiographic measures which confer a mortality benefit.⁶⁻⁸

Although a majority of treated patients show a benefit, up to 40% derive no improvement from CRT. In the MIRACLE study, 34% of patients did not demonstrate an improvement in a HF clinical composite score (CCS) that combined all-cause mortality, HF related hospitalization, NYHA class and patient global assessment into an outcome measure⁹. A summary of non-responder rate from various clinical studies has been performed by Birnie and Tang¹⁰. Those rates of non-response to cardiac resynchronization therapy are often quoted as 20-30% in the listed studies, but the authors suggest that the true non-responder rate may be as high as 40-50%. This inconsistent CRT effectiveness may be due to incomplete resynchronization and the presence of Intraventricular dyssynchrony.

The cause for failed response to CRT is not completely understood; there is a general consensus, supported by growing evidence, that suboptimal LV lead placement accounts for a large percentage of patients who do not respond to CRT.

Some studies have shown that lateral and postero-lateral lead placements have more favorable results than other locations, but the link between lead location and clinical benefit is not yet well understood¹¹⁻¹⁶. Several methods have been used in attempts to optimize lead placement including using intracardiac electrograms to locate the site of most delayed activation, measuring acute hemodynamic response based on lead location; using scar burden and location to predict response; and using electrical mapping to optimize epicardial Left Ventricle (LV) lead placement¹⁷⁻²². However, unfavorable coronary venous anatomy with narrow and tortuous tributaries, phrenic nerve stimulation, high capture thresholds, or pacing lead instability

may limit the use of any of these approaches. Moreover, each of the methods used to optimize LV lead placement to date are time consuming and some are more invasive than the implant itself, imposing potentially higher implant risks. Standard LV lead placement criteria for a stimulation electrode typically focuses on the location of mechanical stability, freedom from phrenic nerve stimulation, reasonable pacing thresholds, or the site of latest electrical activation. However, ischemic cardiomyopathy can cause non-uniform propagation of electrical activity over the myocardium due to scarred myocardial segments and density near the LV stimulation electrode¹². Thus, a site of latest electrical activation may not always yield the optimal response. In such cases, the ability to pace from more than one left ventricular site may provide benefit.

All major medical devices companies offer bipolar LV leads that have one ring electrode and one tip electrode that can be positioned via the coronary sinus. This bipolar LV lead, when used in combination with right ventricular (RV) lead, may have up to six pacing vectors available to the physician for standard biventricular pacing.

St. Jude Medical has developed a new family of quadripolar LV leads which increase the programmability by including one tip electrode and three ring electrodes. This quadripolar lead is called Quartet® LV lead (Model 1458Q, 1458QL, 1457Q, 1456Q and newer). If used with the Unify™ Quadra CRT-D device the system provides 10 different pacing vector options (VectSelect®) from the four pacing electrodes on the LV lead.

Furthermore, this lead allows pacing from any two of the 10 available vectors at the same time in a multi-point fashion (MultiPoint™ pacing or MPP).

MultiPoint™ pacing (MPP) is a new pacing feature in the Quadripolar CRT-D system that allows sequential pacing of the LV with two pacing vectors compared to one vector in a traditional CRT-D system. A combination of any two of the 10 available vectors with inter-stimulus delays can be used. MPP via one LV lead may have the potential to act as an alternative to non-invasively optimize LV lead placement, and it may improve hemodynamics and the response to CRT. Studies showed that simultaneously exciting a larger mass or volume of cardiac tissue results in faster depolarization velocity and shorter left ventricular trans-ventricular conduction times²³⁻²⁴. In addition, by capturing a larger volume of cardiac muscle, the site of latest intrinsic activation within the left ventricle may be more likely to be depolarized early, resulting in better synchronization and maximizing cardiac output.

Since MPP delivers two pulses at programmable delays (LV1 and LV2) to two LV sites, the initial volume of excited cardiac tissue is increased. By capturing more mass at the site of initial depolarization there is a greater likelihood of pacing the site of latest systolic delay. Both of these methods have been shown to improve LV function²⁵⁻²⁶ and it is believed that this additional improvement in LV function may benefit those patients who are otherwise identified as non-responders to conventional BiV pacing.

3 Investigational Design

3.1 Purpose

The purpose of this clinical investigation is to assess the impact of the MultiPoint Pacing (MPP) feature at 12 months in the treatment of patients that are not responding to standard Cardiac Resynchronization Therapy (CRT). Due to a large number of combinations of parameters available for MPP programming, the MPP feature will be evaluated in two scenarios:

- (1) without mandating MPP programming parameters, and
- (2) with mandated MPP programming parameters.

3.2 Objectives

3.2.1 Primary Objective

To demonstrate that the activation of the MPP feature will increase the rate of CRT responders in patients that were already classified as non-responders at 6 months follow up.

3.2.2 Secondary Objectives

To assess the impact of MPP feature on patients functional and clinical status

3.3 Endpoints

3.3.1 Primary Endpoint

The primary endpoint of this study is evaluated at 12 months after enrollment and it is defined as the percentage of non-responder patients converted to responders after 6 months of MPP feature turned ON compared to baseline, as measured by Left Ventricular End Systolic Volume (LVESV) reduction of at least 15%.

3.3.2 Secondary Endpoint

The secondary endpoints of this study are evaluated at 12 months after enrollment and are defined as:

- Reduction of LVESV between baseline and 6 Months visit
- Packer's Clinical Composite Score evaluation between baseline and 12 Months visit and between 6 Months and 12 Months visits
- Reverse LV remodeling, measured as changes in LVESV, LVEDD and LVEF
- NYHA Class changes
- 6 minutes walking test changes
- Quality of Life (MLWHF and EQ-5D) changes

3.4 Investigational Type

This study is designed as a Prospective, Randomized, Multi-center Trial.

Data will be collected at Enrollment, Baseline, Implant Procedure, Patient Classification, 6 Months and 12 Months Follow-Up.

During the Enrollment visit, the Informed Consent Procedure will be performed and the Inclusion/Exclusion criteria verified.

During the Baseline visit the demographic data, medical history, clinical data and procedure details will be collected.

After the Implant Procedure, the Patient Classification will be performed in order to identify the Qualified Subjects that will constitute the Study Population.

During the 6 Months visit, the subject's response to CRT will be evaluated at the center level according to LVESV reduction. Before randomization in the second phase of the study, all subjects will undergo testing to determine if the mandated MPP settings can be programmed (see below for MPP programming requirements in Phase II). For those subjects in whom the mandated MPP settings cannot be programmed before randomization at 6 months, their participation in the study will end (an early termination form must be completed).

- Subjects with a LVESV reduction of at least 15% will be classified as **RESPONDERS**. For those subjects, their participation in the study will end (if confirmed by the Core Lab), and they will then return to the center's routine follow up schedule/practice.
 - If the subject is evaluated as a Responder by the center and later as a Non Responder by the Core Lab, the center must randomize the subject and should call the subject back for an unscheduled visit (see 4.2.7) in case the randomization assignment is different from programmed.
- Subjects with an LVESV reduction of less than 15% will be classified as **NON RESPONDERS**. These subjects should be randomized and the device programmed to either MPP OFF or MPP ON per the randomization assignment (Please refer to section 3.8 "Randomization Procedure" for further details).
 - If the subject is evaluated as a Non Responder by the center and later as a Responder by the Core Lab, the subject continues to 12 Months visit but the data are excluded from the primary endpoint analysis.
- For those subjects randomized to MPP ON in the second phase of the study, the MPP feature should be programmed as follows:
 - MPP Vector combination: Two programmable vectors with widest spacing (≥ 30 mm between two cathodes). The 'Widest Spacing' feature within the VectSelect Quartet™ MultiVector Tools in the Merlin Patient Care System should be used to program to widest spacing.
 - LV1-LV2 delay: 5 ms
 - LV2-RV delay: 5 ms

During the 12 Months visit, the percentage of non-responder subjects converted to responders after 6 months of MPP feature turned ON and MPP feature turned OFF will be assessed:

- Subjects with a LVESV reduction of at least 15% between Baseline and 12 Months will be classified as Responders.
- Subjects with a LVESV reduction less than 15% between Baseline and 12 Months will be classified as Non Responders. Subjects who died due to cardiac cause post randomization will also be classified as Non Responders.

The investigation will be conducted in up to 250 centers worldwide.

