- If the subject is evaluated as a Responder by the center and as a Non Responder by the Core Lab: the center should call back the subject for the randomization procedure (within a reasonable time window (e.g. 2 weeks) after the 6M visit).

Conduction Delays Test:

The conduction delays between right and left ventricle will be performed during implant and each in-clinic follow up. This is an automatic test that can be performed via Merlin PCS programmer and will end in about one minute. Please refer to Appendix E: “Guidelines” part 3 for further details regarding the Conduction Delay test.

Device Test and Programming (EDC upload):

Device will be interrogated and all the diagnostics retrieved; standard sensing, pacing and impedance measurements will be performed for all implanted leads at each in-clinic follow-up. Please refer to Appendix E “Guidelines” part 1.2 for further details on the “Upload Device Data” procedure.

The device programming will be left to Investigator's discretion with the exception of the MPP feature. It is suggested that AV delay optimization is performed per centers' preference.

Please see below the MPP Programming activity.

Follow-up session (including diagnostics) will be uploaded to the EDC system using the feature "Upload Device Data".

MPP Programming:

Overall device programming will be left to the Investigator's discretion with the exception of the MPP feature:

- **MPP should NOT be programmed ON BEFORE** the 6 Months FU
- At the 6 Months FU, the MPP feature will be programmed ON or OFF as per Randomization result (1:1) for subjects classified as NON RESPONDERS according to LVESV reduction less than 15%. Subjects randomized to MPP ON in the second phase of the study should be programmed as follows:
 - MPP Vector combination: Two programmable vectors with widest spacing (≥ 30 mm between two cathodes). The 'Widest Spacing' feature within the VectSelect Quartet™ MultiVector Tools in the Merlin Patient Care System should be used to program to widest spacing.
 - LV1-LV2 delay: 5 ms
 - LV2-RV delay: 5 ms

Please refer to Appendix E: "Guidelines" Part 2 for further details regarding subject's CRT response classification and Part 7 for further details about MPP Programming.

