4.2.3 Implant Procedure (In Clinic, within 30 days from Enrollment)

The implant procedure must be performed within 30 days from the enrollment. SJM MPP compatible CRT system will be implanted with standard procedure.

The following information will be collected at the Implant visit:

- Implant Procedure Details
- Adverse Events and/or Protocol Deviation notification (if applicable)

The following activities will be performed at the Implant visit:

- Device Test and Programming
- Conduction Delay Test
- Fluoroscopy image Collection and upload to EDC portal
- MPP programming (OFF)
- Upload of device session (as .zip-file) to EDC portal

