Subject's response to CRT will be evaluated at the center level using the Preliminary LVESV Evaluation. Before randomization in the second phase of the study, all subjects will undergo testing to determine if the mandated MPP settings can be programmed (see below for MPP programming requirements in Phase II). For those subjects in whom the mandated MPP settings cannot be programmed before randomization at 6 months, the participation in the study will end (an early termination form must be completed).

- Subjects with a LVESV reduction of at least 15% will be classified as **RESPONDERS**. For those subjects, the participation in the study will end (if confirmed by the Core Lab), and they will then return to the center's routine follow up schedule/practice.
- If the subject is evaluated as a Responder by the center and as a Non Responder by the Core Lab, the center must randomize the subject and should call the subject back for an unscheduled visit (see 4.2.7) in case the randomization assignment is different from programmed.
- Subjects with an LVESV reduction less than 15% will be classified as **NON RESPONDERS**. These subjects should be randomized and the device programmed to either MPP OFF or MPP ON per the randomization assignment (Please refer to section 3.8 "Randomization Procedure" for further details).
- If the subject is evaluated as Non Responder by the center and as a Responder by the Core Lab, the subject continues to 12 Months visit but the data are excluded from the primary endpoint analysis.

Subjects randomized to the **MPP ON** group will undergo device programming before leaving the hospital:

- Device programming: MPP feature will be activated and programmed. Please refer to Appendix E: Part 6 and 7 for further details regarding MPP activation and required programming. No further device programming related to dyssynchrony is encouraged unless medically necessary.

- For those subjects randomized to MPP ON in the second phase of the study, the MPP feature should be programmed as follows:
 - MPP Vector combination: Two programmable vectors with widest spacing (≥ 30 mm between two cathodes). The 'Widest Spacing' feature within the VectSelect Quartet™ MultiVector Tools in the Merlin Patient Care System should be used to program to widest spacing.
 - LV1-LV2 delay: 5 ms
 - LV2-RV delay: 5 ms

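### The protocol gives two incompatible call-back and randomisation rules for subjects the core lab reclassifies as non-responders, and one of them makes contact and non-activation depend on arm

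*Combined protocol and SAP*

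**What the plan says.** The centre makes a preliminary reading of LVESV reduction at the 6-month visit, and the Echo Core Lab's reading is final (protocol Sections 3.8 and 4.2). The case at issue is a subject whom the centre calls a responder and the core lab later calls a non-responder. The protocol covers it in three places.

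- **Section 3.4 (Investigational Type):** the centre must randomise the subject and "should call the subject back for an unscheduled visit (see 4.2.7) in case the randomization assignment is different from programmed".
- **Section 4.2.5 (6 Months Follow-Up Visit):** the same rule in nearly the same words: "the center must randomize the subject and should call the subject back for an unscheduled visit", again only where the assignment and the programming differ.
- **Section 4.2 (Preliminary LVESV Reduction Evaluation):** "the center should call back the subject for the randomization procedure (within a reasonable time window (e.g. 2 weeks) after the 6M visit"). The arm plays no part, because the subject has not yet been assigned to one.

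On the device state before randomisation, Section 4.2 (MPP Programming) says "MPP should NOT be programmed ON BEFORE" the 6-month follow-up. Sections 4.2.3 and 4.2.4 list MPP as programmed OFF at implant and at Patient Classification. In Phase II, before randomisation, "all subjects will undergo testing to determine if the mandated MPP settings can be programmed" (Section 4.2.5).

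**The concern.** The two rules differ on who comes back, on whether randomisation precedes the return or takes place at it, and on the time allowed. All three texts are current, and up to 250 centres will apply them, so mixed practice is foreseeable.

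Under Sections 3.4 and 4.2.5, what happens after randomisation depends on the arm. An MPP ON subject must be persuaded to return for an extra device session. An MPP OFF subject hears nothing further until 12 months. If the ON subject does not return, the trial holds a randomised ON subject whose device was never switched. Non-compliance is also a listed reason for withdrawal (Section 5.5). An ON subject who ignores the recall could therefore be withdrawn and leave the primary analysis under Section 7.4, while the matching OFF subject is never put to that test.

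These are core-lab-confirmed non-responders, the group that Section 7.2.1 names for the primary analysis. A randomised comparison should not have arm-dependent contact, non-activation or exclusion built into its own procedure, even in a small subset.

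**Working it through.** No sample size, power or error-rate figure is involved, so the check is a comparison of texts plus day counts.

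**1. When the disagreement becomes known.** Echo transfer takes up to 1 working day and core-lab reading up to 3 (Section 4.2). That is 1 + 3 = 4 working days after the visit, when the subject has normally gone home. Section 4.2.5 also says that subjects randomised to ON are programmed before leaving the hospital; that cannot hold for someone randomised after leaving.

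**2. Who has an assignment different from the programming.** MPP is OFF at implant, OFF at classification and not to be ON before 6 months. Barring a protocol deviation, an assignment can differ from the programming only if it is MPP ON. This is an inference, but a close one.

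**3. The rules side by side.**

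| | Sections 3.4 and 4.2.5 | Section 4.2 |
|---|---|---|
| Order | randomise, then recall if needed | recall, then randomise |
| Who is recalled | in effect, MPP ON only | everyone on this route |
| Time limit | none | two weeks, as an example |
| Does not return, would have been ON | randomised to ON, device stays OFF | not randomised |
| Does not return, would have been OFF | randomised to OFF, no return needed | not randomised |

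Under Section 4.2 the loss comes before allocation and cannot differ by arm. Under the other two sections it comes after allocation and falls on one arm. The Phase II test of mandated settings applies to all subjects before randomisation, so it does not separate the arms.

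**4. Exposure time, to see whether it distinguishes the rules.** The 6-month visit is at day 183 ± 14 (169 to 197) and the 12-month visit at day 365 ± 21 (344 to 386). Both are counted from implant.

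- Nominal exposure: 365 − 183 = 182 days.
- Range over the windows: 344 − 197 = 147 to 386 − 169 = 217 days.
- With a 14-day recall: 182 − 14 = 168 days nominal (14/182 = 7.7% less); range 133 to 203 days.

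An ON subject who has gone home must return for programming under either rule, and the 12-month visit does not move. The shortening is therefore common to both rules and is not a consequence of choosing one of them.

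**5. What remains.** Let D be the ON-minus-OFF difference in response if all ON subjects are activated. Let u be the fraction of the analysed ON arm that is never activated by this route. If those subjects respond as controls do, the expected difference is D × (1 − u). The fraction u depends on how often the readings disagree in this direction, how often ON subjects fail to return, and how many of those still attend at 12 months with a valid echo. The documents give none of the three.

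**The case against.** The strongest reply is that this is a wording slip with little consequence. Several larger consequences that a reader might infer are not supported.

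- **Lost exposure.** A reader might blame the conditional recall for the range of 133 to 203 days. Step 4 of the working shows that the delay arises under either rule and would remain after reconciliation.
- **A sizeable untreated share.** If one assumes that 5–15% of randomised subjects come by this route and that 10–30% of those assigned ON do not return, then 5% × 10% = 0.5% to 15% × 30% = 4.5% of the ON arm is never activated. Nothing in the documents anchors either range. Section 7.4 also excludes subjects who do not complete follow-up for reasons other than cardiac death, or who lack valid LVESV data, so only non-returners who attend at 12 months would dilute the result. Even at 4.5%, an assumed difference of 10 points would become 10 × (1 − 0.045) = 9.55.
- **Disclosure of allocation.** Being recalled would tell the subject the arm, but the readable text states no blinding of subjects, so there is no stated protection to breach.
- **Mortality curves.** SAP Section 6.2 starts the clock at randomisation. The two rules could move that date, but within either rule it means the same thing in both arms.
- **Contact effects.** One unscheduled visit, nominally 168 days before the 12-month assessments after a 14-day recall, is unlikely to move a volume threshold on which the core lab's reading is final. An effect on NYHA class, patient global assessment or quality of life is possible, but its direction and size are unknown.
- **Missing analyses.** The SAP cohort definitions (5.1.2), sensitivity analyses (5.1.4) and supplemental analyses (5.1.7) are redacted, so a separate look at these subjects cannot be called absent.

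All of this stands, and it limits the size of the problem. It does not remove the contradiction. One could read Section 4.2 loosely, as a recall for programming after a remote randomisation, but it says the recall is for the randomisation and makes no exception for subjects who would be assigned OFF.

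**Conclusion.** Wrong as written: the protocol holds two randomisation procedures for the same subjects. Severity is low to moderate. What is established is the conflict itself, together with the fact that following Sections 3.4 and 4.2.5 makes contact, non-activation and possibly exclusion depend on arm, whereas following Section 4.2 does not.

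This rests on two assumptions: that MPP is OFF in these subjects as the protocol requires, and that some centres apply Sections 3.4 and 4.2.5 literally. The size of the subset is not stated. The effect on the primary result is probably small if recalls are prompt and most subjects return, but it cannot be quantified from the documents. Late or absent activation would tend to dilute an MPP effect; extra contact could act in either direction.

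**What to change.** Reconcile Sections 3.4, 4.2 and 4.2.5 into one procedure that is the same for both arms. Every subject on this route attends a call-back visit, randomisation is done and dated at that visit, and a stated time limit replaces the present mix of none and an example. A subject who does not attend is then not randomised, so non-attendance at the call-back cannot differ by arm. This concerns the conduct of randomisation only and implies nothing about how the device should be programmed.

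Record a flag for subjects who enter by this route. If the redacted SAP sensitivity analyses do not already do so, show the primary result with and without them. The route is fixed by the two echo readings before allocation, so leaving these subjects out keeps the comparison randomised.

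The cost is protocol wording, one data field and one short visit for the MPP OFF subjects on this route. Section 4.2 already asks for that visit.
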